specialized in therapy against lung diseases taught patients pulmonary expansion exercises to be carried out until surgery was performed. Smoking cessation and nutritional screening of the patient were also part of this stage.

The patients underwent video-assisted thoracoscopic surgery (VATS), whenever possible, leaving a chest tube at the end of the surgery. All subjects received antibiotic and antithrombotic prophylaxis. Intraoperative management of patients was performed under general anaesthesia combined with regional techniques for pain control, avoiding the use of benzodiazepines and opioids. Those patients in whom thoracic epidural catheter was implemented during surgery continued its use through a patient-controlled analgesia system. Besides, a hot air system warmed the patients during surgery to maintain normothermia. Extubation was performed as soon as possible after the end of the surgery, and we encouraged early removal of the urinary catheter.

From the time of extubation, the patients began oral tolerance and respiratory physiotherapy exercises. Also, the patients were allowed to walk around early. The patients were discharged when they were free of complications, without severe pain, urinary catheter or chest tube.

Outcomes

The primary outcome was the number of patients with 30-day surgical complications. We defined air leakage, bleeding, infection, and reintervention as surgical complications. Secondary outcome included ERAS adherence, no-surgical complications, mortality, readmission, reintervention rates, pain (defined as any level of pain that prevents early ambulation) and hospital lenght of stay. To evaluate ERAS adherence, we defined seven items: VATS approach, regional analgesia, oral tolerance within 6 hours, urinary catheter removal within 24 hours, ambulation within 24 hours, respiratory physiotherapy within 24 hours and chest tube removal within 48 hours.

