## Statistical analysis

We analyzed outcomes depending on whether the patient belonged to the ERAS program or the retrospective standard cohort. The discrete and continuous variables were described as number and percentage and median (interquartile range [IQR]) and their differences analyzed using the Pearson test or the Wilcoxon rank-sum tests. Subsequently, according to the adherence rate to ERAS items (regardless of whether the patients belonged to the ERAS or the retrospective standard cohort), We performed a multivariate logistic analysis to study the association of complication rates, readmission or pain with ERAS adherence, clinical and demographic data, presenting the results in forest plots as odds ratio with 95% confidence interval. Similarly, we used Cox regression for multivariate analysis of length of stay, presenting the results in forest plot as hazard ratio with 95% confidence interval. To avoid errors by multiple comparisons, we calculated the respective q-value for each p-value to maintain a false discovery rate below 5%. We considered comparisons in which p-value and q-value were below .05 as being statistically significant.

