## RESULTS

No patient declined inclusion in the study. The demographic characteristics and comorbidities of the patients are shown in Table 1. The two cohorts were not totally homogeneous, with a higher number of patients with hypertension in the standard cohort [26 (52%) vs ERAS 15 (30%),  $p = 0.03$ ] and chronic obstructive pulmonary disease [12 (24%) vs ERAS 4 (8%),  $p = 0.02$ ]. Although the number of patients with ASA class  $> 2$  was higher in the standard group [26 (52%) vs ERAS 15 (30%)], we found no difference between the cohorts in Charlson's comorbidity index. We included these three items, along with age and sex in the subsequent multivariate analyses.

Data on ERAS adherence and compliance for each of the protocol items are shown in Table 2. Adherence to the ERAS protocol was significantly higher in the prospective than in the retrospective cohort [Median: Standard 0.29 (0.14-0.43) vs ERAS 0.71 (0.57-0.82),  $p < 0.001$ ]. The VATS approach was greater in the ERAS group [29 (58%) vs Standard 11 (22%),  $p < 0.001$ ], and the number of patients who ambulated on the first postoperative day [40 (80%) vs Standard 0 (0%),  $p < 0.001$ ], but no difference was found in the use of regional analgesia. Also, the times to oral intake and removal of the urethral catheter were lower in the ERAS group [Median (h): Standard 24 (24-24) vs ERAS (6-7.5), and Standard 48 (24-48) vs ERAS 19 (6-24), respectively].

The primary and secondary results are shown in Table 3. We found no difference between the two groups in either surgical complications [Standard 18 (36%) vs 12 (24%),  $p = 0.19$ ], non-surgical complications [Standard 21 (42%) vs 12 (24%),  $p = 0.06$ ] or length of stay [Median (days): Standard 4 (3-6) vs 4 (3-5),  $p = 0.19$ ], and the ERAS group was significantly lower only in its readmission rate [Standard 15 (30%) vs 6 (12%),  $p = 0.03$ ]. No deaths were recorded in the ERAS group, compared to two deaths in the retrospective cohort.

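### The adherence score used to explain pain includes ambulation within 24 h, while pain is defined by prevented early ambulation; for length of stay it includes chest tube removal, which the discharge rule requires

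*Protocol*

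**What the plan says.** The Protocol (Outcomes) scores adherence on seven items. The last three are "ambulation within 24 hours, respiratory physiotherapy within 24 hours and chest tube removal within 48 hours"; the catheter item (urinary catheter out by 24 h) is another. The same section lists among the secondary outcomes "pain (defined as any level of pain that prevents early ambulation", without saying what counts as early. The Protocol (Procedures) gives the discharge rule: "The patients were discharged when they were free of complications, without severe pain, urinary catheter or chest tube".

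The SAP (Statistical analysis) fits logistic models for complications, readmission and pain "according to the adherence rate to ERAS items (regardless of whether the patients belonged to the ERAS or the retrospective standard cohort", and adds: "Similarly, we used Cox regression for multivariate analysis of length of stay".

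The SAP (RESULTS) reports "the number of patients who ambulated on the first postoperative day [40 (80%) vs Standard 0 (0"%). For adherence it gives an OR of 0.01 (0.00 to 0.28) for pain, an OR of 0.01 (0.00 to 0.24) for readmission and an HR of 18.5 (4.39 to 78.4) for discharge. The available text describes no step that leaves an overlapping item out of the score. Tables, figures and one part of the SAP are not in that text, so this statement covers only what can be read.

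**The concern.** An exposure should not contain information about the outcome that it is used to explain. For pain it seems to do so: a patient is a pain case only if pain stopped early ambulation, and a patient who did not ambulate in time loses an adherence point. Covariate adjustment cannot remove this, because it is not confounding; part of the outcome is inside the exposure.

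For length of stay the link is weaker in kind. Stay is not defined through the chest tube. The tube enters through the discharge rule, so the hazard of discharge is partly related to having met a condition for discharge.

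What is at stake is the reading of the adherence models. For stay, the direct cohort comparison shows no difference, "length of stay [Median (days): Standard 4 (3-6) vs 4 (3-5"), p = 0.19, so the favourable message about stay rests on the adherence model alone.

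**Working it through.** **Planned figure.** The only planned figure is 47 per arm. It is reproduced by the two-sided unpooled normal formula for 40% vs 15%: (0.40×0.60 + 0.15×0.85)×(1.96 + 0.842)²/0.25² = 46.2, rounded up to 47. It does not depend on the adherence score.

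**Pain: what the definitions imply.** Take *early* to mean the scored item, and the reported first-postoperative-day figure to measure that item. Then:
- ERAS cohort: 50 − 40 = 10 patients did not ambulate. Every ERAS pain case is among these 10, so the ERAS pain rate cannot exceed 10/50 = 20%.
- Standard cohort: 0 of 50 ambulated. All 50 lose the point whether or not they had pain, so the item cannot separate pain cases there. Between cohorts (0% vs 80%) it is close to a cohort marker.
- Each pain case lacks 1/7 = 0.14 of the score.

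**Pain: size under a true null.** Simulation with 50 + 50 patients, ambulation 40/50 vs 0/50, pain equally common in both cohorts and unrelated to the other six items. Rates from the SAP (standard/ERAS): VATS 0.22/0.58. Assumed rates: regional analgesia 0.70/0.70, oral tolerance 0.05/0.65, catheter 0.35/0.80, physiotherapy 0.40/0.90, tube 0.35/0.50. These give median scores of 0.29 and 0.71, as reported. The logistic model has adherence (0 to 1) plus five noise covariates, without/with epidural and intercostal terms; 3000 replicates.

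| Assumed pain rate | Seven-item OR | p < 0.05 |
|---|---|---|
| 5% | 0.31 / 0.33 | 3.2% / 2.5% |
| 10% | 0.34 / 0.31 | 6.6% / 7.0% |
| 15% | 0.33 / 0.30 | 11.0% / 11.6% |
| 20% | 0.31 / 0.28 | 14.7% / 16.3% |

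Without ambulation, at 10-20% pain, the OR is 0.99-1.02 with 4.0-5.6% rejection. Two further simulations of this null at 10/15/20% gave seven-item ORs of 0.38/0.32/0.32 and 0.35/0.32/0.32, with 6-14% rejection. Without ambulation they gave 0.96-1.10 with 3-4.5%.

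**Pain: what a refit leaves behind.** Now let pain occur in 20/40/60% of non-ambulators in either cohort. Pain then differs by cohort: 20/40/60% in the standard cohort, against 10/50 of that, 4/8/12%, in ERAS. The seven-item OR is 0.06/0.04/0.015. Without ambulation it is still 0.11/0.08/0.04, because the other items track cohort. With cohort also in the model, the score without ambulation gives about 0.9-1.0.

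**Stay: two mechanisms.** Cox model, same item rates unless stated, stay quartiles about 3/4/5 days.
- *Shared recovery, tube removal without effect on discharge.* Assumed correlation 0/0.5/0.8 gives HR 0.96/1.50/1.91 with 6.4/16.2/31.8% rejection. Without the tube item: 0.96/0.99/1.00 with 5.7/6.1/5.2%.
- *Genuine gating, no shared cause.* If the tube is the last condition met in 19% of patients, HR is 1.16, and 1.07 without the tube item. If in 53% (assumed tube rates 0.20/0.35), 2.34 and 1.60. These are mediated effects, not false positives.

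**Urinary catheter.** It too is both an adherence item and a discharge condition. Removal times are "Standard 48 (24-48) vs ERAS 19 (6-24), respectively" (hours), and the lower quartile of stay is 3 days (72 h) in both cohorts. So at least three quarters had the catheter out by 48 h or 24 h, while about three quarters stayed 72 h or longer. This suggests that the catheter seldom holds up discharge. It does not prove it: marginal quartiles say nothing about the slowest quarter or about joint timing. With catheter times fitted to those quartiles, it was last or jointly last in 3-7% of simulated patients.

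**Against the reported ratios.** If the score is coded 0 to 1, the effect per item is 0.01^(1/7) = 0.52 (upper limit 0.28^(1/7) = 0.83) for pain, 0.52 (upper 0.24^(1/7) = 0.82) for readmission, and 18.5^(1/7) = 1.52 (1.24 to 1.86) for discharge. Readmission shares no definition with any item, yet its ratio is the same as that for pain.

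**The case against.** The case on the other side has several strong parts.

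- *The pain overlap is conditional.* The Protocol does not define early. This stands, and is itself a reason for a definition.
- *Early tube removal is part of the programme, so counting it as adherence is defensible.* This stands. The stay bias appears only under an assumed recovery correlation for which the documents give no value. The discharge rule also sits within the description of the ERAS programme, and the documents do not say whether it governed the 2016 cohort. The stay point is therefore a caveat about interpretation.
- *The authors already speak of associations.* True, but an association partly built into the definitions still misleads.
- *A refit without ambulation does not isolate adherence from cohort.* True, as the second pain simulation shows. It removes the definitional part only.

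A reader might infer that the overlap explains the OR of 0.01 and the HR of 18.5. The documents do not support that: no null scenario with equal cohorts reaches either figure, and readmission shows the same OR without overlap. A reader might also extend the point to surgical complications, reasoning that an air leak keeps the tube in. That is clinical inference; neither document states the link.

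**Conclusion.** The pain point holds, on the condition that early means the scored 24 h item. The seven-item pain model then contains part of its own outcome and is biased towards a favourable association: under equal pain rates of 10-20%, a null OR of about 0.3 with about 6-16% false positives, against about 1.0 with about 3-6% once ambulation is left out. At 5% pain the OR is equally displaced but rejection is not inflated.

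For length of stay, the adherence HR partly reflects meeting a discharge condition. Whether that is benefit or bias cannot be told from the seven-item model, and confidence here is lower.

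The size in this study is unknown without patient-level data; pain rates, tube rates and most other item rates above are assumptions. The cohort comparisons, including the primary outcome (36% vs 24%, p = 0.19), do not use the score and are unaffected. The point should be fixed, but it does not overturn the study.

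**What to change.** Define early ambulation in the pain outcome, and state the scale on which the score enters the models, so that ratios from different versions of the score can be compared. Then add to the SAP, in words such as:

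*Adherence is the proportion of the seven items met. Beside the seven-item results, the pain model is refitted with the score without ambulation, and pain is interpreted from that refit. As a sensitivity analysis, the length-of-stay Cox model is refitted with the score without chest tube removal, and again without both chest tube and urinary catheter removal. A weaker hazard ratio may also reflect the loss of a genuine benefit through earlier removal. These refits are post hoc; they remove definitional overlap only and do not remove confounding by cohort.*

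Also say whether the refits enter the q-value calculation. No refit of the surgical-complications model is needed on this ground.

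The cost is a few extra models on data already collected and a few sentences; no patients are lost. The pain and stay associations will probably be weaker, and the reduced scores no longer test the dropped component for that outcome.

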Implementation of an ERAS program in patients undergoing thoracic surgery at a third-level university hospital. An ambispective cohort study.

(Short title: ERAS implementation in thoracic surgery)

31/12/2019

NCT ID not yet assigned

METHODS

Study design and participants

This study analyzes the implementation of an ERAS program in a thoracic service of a third level hospital (*Hospital Fundación Jiménez Díaz, Madrid, Spain*). To this end, we designed an ambispective cohort study, with a prospective arm of patients undergoing thoracic surgery within an ERAS program versus a retrospective arm of patients before the implementation of the protocol. Our centre's ethics committee approved our study before the start of patient recruitment, January 2018 Ref: EO071-18_FJD. This study followed the Strengthening the Reporting of Observational Studies in Epidemiology ([STROBE](#)) reporting guideline for cohort studies¹³.

After informed consent, we included patients consecutively since the implementation, except those who refused the inclusion in the study or were under 18 years old. We also asked for informed consent from the patients who were part of the retrospective cohort. For the calculation of the required sample size, we assumed that the ERAS program would result in a 25% reduction in the absolute risk of suffering a surgical complication. Since the surgical complication rate for our patients in 2016 was 40%, a type-I error of 5% and a power of 80% would require 47 patients per arm.

Procedures

We recruited 50 patients throughout 2018 and 2019 and compared them with data from the last 50 patients in 2016, the year in which we knew the surgical complication rate. We followed up each patient for 30 days after surgery through hospital and primary care medical records. Demographic and comorbidity data were collected from all patients, from which we calculated Charlson's comorbidity index¹⁴ for all patients.

We designed our centre's ERAS program through different measures during the preoperative, intraoperative and postoperative period. During the preoperative period, the patients and their families received comprehensive multidisciplinary information about the protocol, as well as their daily goals and expected discharge date. Also, a team

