Multivariate analyses are shown in Figures 1, 2 and 3. ERAS adherence was the only factor associated with a reduction in surgical complications [OR (95%CI) = 0.02 (0.00, 0.59),  $p = 0.03$ , Figure 1A], and postoperative pain [OR (95%CI) = 0.01 (0.00, 0.28),  $p = 0.01$ , Figure 2B]. It was also associated with a lower readmission rate [OR (95%CI) = 0.01 (0.00, 0.24),  $p = 0.007$ , Figure 2A] and an increased likelihood of discharge from the hospital [HR (95%CI) = 18.5 (4.39, 78.4),  $p < 0.001$ , Figure 3]. The thoracic epidural analgesia was the only factor that showed an association with lower rates of non-surgical complications [OR (95%CI) = 0.09 (0.01, 0.49),  $p = 0.008$ , Figure 1B]. It was also associated with lower rates of postoperative pain [OR (95%CI) = 0.16 (0.03, 0.86),  $p = 0.03$ , Figure 2A] and increased probability of discharge from the hospital [HR (95%CI) = 3.14 (1.39, 7.07),  $p = 0.006$ , Figure 3]. The intercostal blockade also increased the latter likelihood [HR (95%CI) = 7.55 (2.94, 19.3),  $p < 0.001$ , Figure 3].

No significant  $p$ -value was rejected after the calculation of  $q$ -value within the multiple comparability study.

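### A complication in the first 48 hours can itself lower the adherence score, so the adherence odds ratio for surgical complications is open to bias away from 1

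*Protocol*

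**What the plan says.** **Exposure.** In the Protocol (Outcomes), "we defined seven items: VATS approach, regional analgesia, oral tolerance within 6 hours, urinary catheter removal within 24 hours", followed by "ambulation within 24 hours, respiratory physiotherapy within 24 hours and chest tube removal within 48 hours". VATS approach and regional analgesia are settled by about the end of surgery. The other five items are settled 6, 24, 24, 24 and 48 hours later.

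**Outcome.** "The primary outcome was the number of patients with 30-day surgical complications". The components are given as "We defined air leakage, bleeding, infection, and reintervention as surgical complications". Neither a minimum duration nor an earliest onset is set. On follow-up, the Protocol (Procedures) states: "We followed up each patient for 30 days after surgery through hospital and primary care medical records".

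**Model.** The SAP (Statistical analysis) pools the two cohorts and states: "We performed a multivariate logistic analysis to study the association of complication rates, readmission or pain with ERAS adherence". The available text contains no landmark, no rule for early events and no analysis limited to items settled before the outcome can occur.

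**Result.** The SAP (RESULTS) reports that "ERAS adherence was the only factor associated with a reduction in surgical complications", with OR 0.02 (0.00 to 0.59), p = 0.03. The direct cohort comparison of the same outcome was 18/50 against 12/50, p = 0.19.

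**The concern.** The exposure and outcome windows overlap for the first 48 hours. A patient who bleeds, leaks air or returns to theatre in that time may miss ambulation, oral intake, physiotherapy or tube removal because of the complication. Such a patient enters the model as low adherence with an event, exactly like a patient whose low adherence came first. The model cannot tell the two apart, and adjusting for age, sex and comorbidity does not restore the time order.

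At stake is the only positive finding on the primary outcome. The cohort comparison, which this problem cannot affect, shows no difference. The adherence OR is worded as a reduction in complications, yet part of it may reflect complications reducing adherence.

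**Working it through.** **1. The reported figures.** SE of the log OR = (ln 0.59 − ln 0.02)/1.96 = (−0.528 + 3.912)/1.96 = 1.73. Then z = −3.912/1.73 = −2.27 and p ≈ 0.023. The report gives 0.03 from rounded inputs, so the figures agree.

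Cohort contrast: OR = (12 × 32)/(38 × 18) = 384/684 = 0.56. SE = √(1/12 + 1/38 + 1/18 + 1/32) = 0.443, so the 95% CI is 0.24 to 1.34. Pearson χ² = 100 × (384 − 684)²/(50 × 50 × 30 × 70) = 1.71, p = 0.19, as reported.

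**2. Scale.** RESULTS gives median adherence as a proportion, 0.29 and 0.71. If the model uses that 0–1 scale (an assumption), 0.02 compares 7 items with none. That is 0.02^(1/7) = 0.57 per item and 0.02^0.42 = 0.19 across the gap between the medians. Taken causally, odds of 0.36/0.64 = 0.5625 become 0.5625 × 0.193 = 0.109, a rate of about 10% (5/50). The ERAS cohort had 12/50. At the upper limit of 0.59 the predicted rate is about 31%, so this is a signal and not proof.

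**3. Simulation, equal risk and no effect of adherence.** Each study has 50 + 50 patients, item compliance of about 30% and 68% by cohort, and a 30% complication risk for everyone. An early complication sets a fixed number of items to not met. Complication is then regressed on adherence (0–1), unadjusted. The share of early complications is not in the documents, so a range is shown. Small ranges within a cell are variation between repeat runs.

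| Share early | Items blocked | Median OR | False protective result (p < 0.05, OR < 1) |
|---|---|---|---|
| none | – | about 1 | 2–3% |
| half | 1 | 0.55–0.59 | 7–9% |
| half | 2 | 0.31–0.35 | 22–24% |
| half | 3 | 0.19–0.20 | 43–46% |
| three quarters | 1 | 0.41–0.44 | 13–16% |
| three quarters | 2 | 0.17–0.19 | 43–46% |
| three quarters | 3 | 0.07 | 81% |
| all | 3 | about 0.02 | – |

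A blocked item may already have been unmet. Three blocked items are therefore a net loss of about 3 × (0.30 + 0.68)/2 ≈ 1.5 items.

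**4. Simulation, observed 18 and 12 events.** VATS (22%/58%) and ambulation (0%/80%) are taken from RESULTS. The other item rates are assumed, in three sets that each match the reported median adherence. Adherence again has no effect.

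| Reverse mechanism | Median OR |
|---|---|
| none | 0.41–0.44 (0 of 1,000 runs at or below 0.025) |
| all complications early, tube item only | 0.11–0.25 |
| half early, tube item plus each other postoperative item with probability 0.5 | about 0.10 |
| 70% early, same loss | 0.04–0.05 |
| all early, tube item plus each other item with probability 0.3 | 0.03–0.05 |
| all early, tube item plus each other item with probability 0.5 | 0.009–0.015 (74–88% of runs at or below 0.025) |

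The last row is a net loss of 1.1 to 1.4 items per complicated patient. With 15 and 15 events and that same mechanism, the median is 0.02 to 0.03.

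**The case against.** - **No onset data.** The documents give no onset times, no count by type of complication and no patient-level adherence. A reader might infer that the OR is biased by design, or that 0.02 is an artefact. The documents do not support either: they show that the bias can occur, not that it did or how large it was. This stands.
- **Air leak.** A reader might also infer that air leak, through delayed tube removal, accounts for the result. The text available says neither how many complications were air leaks nor that leaks delayed removal; the link is clinical reasoning. The tube item alone gives a median of 0.11 to 0.25. This stands too.
- **Extreme scenarios.** With half of complications early, the median stays well above 0.02. This stands for the point estimate. However, the reported interval reaches 0.59 and so contains many of the milder results, and false protective findings rise well before the extreme cases.
- **Unadjusted simulation.** The reported model has covariates, so the simulated ORs show the mechanism and are not estimates of the bias in that model.
- **Wording and place.** The SAP speaks of association, puts the cohort comparison first and reports it plainly as no difference. That is fair. But calling the association a reduction leans towards cause, and nothing warns the reader about time order.
- **Fragile landmark model.** There are 30 events. If half are early, about 15 remain for adherence and five or more covariates. This stands, and it is why a landmark model should not be the only replacement.

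**Conclusion.** The concern holds as a defect of the analysis: followed as written, the model can return a protective OR when adherence has no effect. With half of complications early and 1 to 3 items blocked, the median OR is about 0.6 to 0.2 and the false protective rate about 7% to 46%, against 2.5% nominal. A median near 0.02 needs essentially all complications early with about three items blocked or, with the observed 18 and 12 events, most of them early with several items affected.

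The actual bias is unknown. The figures rest on assumed early shares, assumed rates for most items, independent items and no covariates. Confounding by patient or surgical severity could act in the same direction and is not separated here. The cohort contrast, OR 0.56 (0.24 to 1.34), is free of this particular problem.

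**What to change.** 1. Extract the onset of each complication from the records already reviewed, where recorded, and report the numbers before and after 48 hours by cohort.
2. For all 30-day surgical complications, and likewise non-surgical ones, make the time-ordered analysis one that uses only the items fixed by the end of surgery (VATS approach, regional analgesia) as exposure.
3. As a sensitivity analysis, score full adherence at 48 hours and model complications starting later, in patients alive and free of that complication at 48 hours. Use few or penalised covariates.
4. Present the cohort contrast (36% vs 24%, p = 0.19; crude OR 0.56, 95% CI 0.24 to 1.34) as the main result on the primary outcome. Reword RESULTS so that the adherence OR is an association whose time order is not established.

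**Cost.** One further reading of the charts and one re-analysis. The landmark analysis will have fewer events and a much wider interval, and onset dates may be incomplete for the 2016 cohort. The two-item exposure gives up most of the adherence score and remains open to confounding by severity. Steps 2 and 4 need no new data.
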